Aim 3: Determine which factors affect the antibody response post-vaccination. Using vaccine studies from the past decade, we have quantified how various factors (e.g., age, sex, BMI) affect the antibody response. In this study, we are adding two additional factors within our questionnaire – how much do you exercise and how much sleep did you get the night before – that have been demonstrated to affect the vaccine response to influenza and other pathogens [Rayatdoost 2022, *Yale J Biol Med*]. Comparing this cohort to other publicly available vaccine studies, we will quantify the impact of both features in the vaccine response.

June 2024 Amendment

Aim 4: Does administering the 2023 vaccine late in the season prime the subsequent 2024 response? By comparing antibody responses in our cohort versus responses from other influenza vaccine studies (where participants are annually vaccinated), we will quantify whether this prime-boost regime leads to fundamentally stronger or longer-lasting responses.

7. Background and Significance

Provide relevant background information to justify performing the proposed study. Describe any relevant preliminary data. Indicate the significance of the research based on the existing literature and how will it add to existing knowledge.

The unparalleled impact of the ongoing COVID-19 pandemic and the four pandemics caused by influenza viruses over the past century underscore the significant threat respiratory viruses pose to human health. By the end of 2023, COVID-19 had resulted in over 100 million infections in the United States alone (WHO). Similarly, influenza caused ~26 million infections in 2022-23 and ~45 million infections in 2023-24 thus far (CDC). One of the major challenges we face, if we wish to successfully combat a future pandemic, is the establishment of strong and durable immune memory against these viral threats. Currently, both SARS2 and influenza viruses evade vaccine induced responses and must be regularly reformulated to generate protective immunity, yet the repercussions of the many choices that must be made during vaccine selection, especially the choice of the vaccine's composition, remain poorly understood. Quantifying the differences between individuals receiving the 2023 and 2024 vaccines as close together in time as possible will clarify the effect of changing the vaccine.

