The [name] lab has developed a unique framework to use baseline (day 0) antibody inhibition profiles to predict the subsequent response at day 28 and day 90 post-vaccination. Our models are trained using prior vaccine studies to predict the outcomes of future responses. We have demonstrated our predictive power on influenza vaccine data from every season from 2014-15 to 2023-24 and used these methods to quantify the different effects from each year's vaccine. For example, we found that the 2023 vaccine elicited ~2x lower fold-change in H3N2 serum hemagglutination

compared to the 2022 vaccine (even though both contained the same H3N2 vaccine strain), demonstrating that the immune background can substantially affect the vaccine response.

Using this cohort, we will quantify the vaccine responses between: (1) previous vaccine studies administered last fall using the 2023 vaccine, (2) our late-season study administering the 2023 vaccine, and (3) future vaccine studies next fall administering the 2024 vaccine. In each case, we will analyze the peak vaccine response (at day 28) and its durability (by assessing vaccine waning at day 90) as well as quantify how accurately each vaccine cohort can predict the other cohorts to disentangle the effects of exposure background and vaccine composition. In doing so, we will demonstrate a means to rigorously assess vaccine responses across seasons without the confounding effects of different immune backgrounds.

June 2024 Amendment: Using the cohort from this study, we will quantify the vaccine responses of people receiving the influenza 2024 vaccine whose previous vaccine was either administered: (1) in May/June [our late-season vaccine study] or (2) in the Fall of 2023 [using other annual vaccine studies]. In each case, we will analyze the peak vaccine response (at day 28) and its durability (by assessing vaccine waning at day 90) as well as quantify how accurately each vaccine cohort can predict the other cohorts. Our goal will be to demonstrate whether such late-season vaccine administration can boost subsequent vaccine responses.

8. Estimated Duration of the Project

State the duration of the entire study from opening of study for participant recruitment through end of follow up and data analysis to project completion.

We estimate the study will take 10 years starting in 2024 and ending in 2034.

9. Subject Population

Describe the characteristics of the proposed subject population.

Include:

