1. Total number of participants to be studied
2. Age
3. Gender
4. Ethnic background
5. Health status

State the inclusion and exclusion criteria for participants to be enrolled on this study.

Indicate whether any vulnerable groups such as children, pregnant women, prisoners, adults unable to consent will be included and provide rationale for involving such participants.

We anticipate enrolling 25-60 donors. Study participation will not be limited to donors of any specific race or ethnic background.

June 2024 Amendment: Only donors who received the late-season 23-24 vaccine will be eligible to continue and receive the 2024-25 vaccine in Sep-Nov, since we only want participants who had been given a late-season influenza vaccine.

Inclusion Criteria

All of the donors will correspond to the following criteria:

- Be between 18-64 years of age
- Males or non-pregnant, non-nursing females
- Weigh at least 85 pounds for whole blood draw
- Ability to provide signed informed consent
- Subjects must plan to receive the intramuscular influenza vaccine at LJI

Vaccinated at LJI:

All subjects will receive the approved intramuscular quadrivalent Fluzone influenza vaccine for the 2023 season at LJI. Enrollment will begin in May, and subjects will receive their vaccine before its expiration date at the end of June 2024. Every year the LJI clinical core offers a seasonal influenza vaccination program for LJI employees, the Clinical Core licensed nursing staff are trained in administering these vaccines. All vaccinations are administered under current standing orders on file by the LJI Medical Director, [name].

June 2024 Amendment: All subjects will now receive the approved intramuscular quadrivalent Fluzone influenza vaccine for the **2024 season** at LJI. These vaccines will be administered before December 2024.

Exclusion Criteria:

All of the donors will correspond to the following criteria:

- Received an influenza vaccine in the past year
- HIV, HBV, HCV infection
- History of certain anemias
- Presence of significant cardiovascular disease, systemic diseases including, but not limited to, diabetes which is not controlled, renal disease, liver disease, malignancy, infection, or blood clotting disorder
- Inability to provide informed consent
- Recent whole blood donation within 56 days or leukapheresis within 112 days
- Children (under 18 years of age), elderly (65 years of age or older), pregnant or nursing females
- Individuals with egg allergies

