Human subjects protocol narrative – Version 2.1 August 17th 2021

- If yes- When were you diagnosed with influenza?
- Have you ever had an adverse reaction to a dose of influenza vaccine? (Yes/ No)
- Do you have an allergy to eggs? (Yes/ No)
- Have you received another vaccine (not an influenza vaccine) in the past 14-days? (Yes/ No)
 - If yes- What vaccine did you receive?
 - If yes- When did you receive the vaccine
- Do you have any illnesses that would give you concern during a blood donation?

An IRB approved flyer may be shared with friends, colleagues, on LJI's website or to anyone expressing interest in participating in LJI's clinical research.

Participants will be welcome to withdraw from the study at any point. Moreover, we will analyze the samples as they are received, and if the day 0 or day 28 samples show no measurable serum inhibition we will not proceed with the subsequent time points. In addition, if the number of subjects we enroll is <25 either at the beginning of the study or because of drop-out, we may opt to not proceed with subsequent time points. Fewer than 25 participants would not yield enough data points for meaningful results.

11. Study Design and Methods

Describe the research design and the procedures to be used. Clearly describe what a subject in this study can expect to happen to them. Include a clear description of the procedures/activities associated with the study including where the procedures/activities will be done, what will be done at each study visit, as well as the participant's time commitment for each study visit and the total duration of the participant's involvement in the research. If questionnaires/surveys will be completed as part of the research, a copy should be included with the protocol submission.

Describe the type of analysis to be performed on biospecimens/collected data. Indicate whether any genetic analysis is to be performed or any cell lines are to be created.

Indicate whether any test or experiment results will be returned to subjects.

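### Raw cross-cohort prediction accuracy cannot by itself separate exposure background from vaccine composition, because it also falls when this 25-60 person cohort is the training set

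*Protocol*

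**What the plan says.** Section 7 (Background and Significance) describes models that "use baseline (day 0) antibody inhibition profiles to predict the subsequent response at day 28 and day 90 post-vaccination". It names three cohorts: fall recipients of the 2023 vaccine, this study's late-season recipients of the 2023 vaccine, and fall recipients of the 2024 vaccine. Peak response and waning will be compared among them. The protocol will also "quantify how accurately each vaccine cohort can predict the other cohorts to disentangle the effects of exposure background and vaccine composition". The paragraph concludes that "we will demonstrate a means to rigorously assess vaccine responses across seasons without the confounding effects of different immune backgrounds".

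On size, section 9 says "We anticipate enrolling 25-60 donors". Section 10 gives the reason for the lower limit: "Fewer than 25 participants would not yield enough data points for meaningful results". No derivation accompanies either figure.

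On who is compared, section 9 excludes anyone who "Received an influenza vaccine in the past year". Aim 4 in section 6 describes its comparison studies as ones in which people are vaccinated every year. For the three-cohort comparison the comparators' vaccination histories are not stated.

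**The concern.** There is no randomised comparator, so any attribution to formulation or to exposure history has to come from comparing cohorts recruited at different times. Section 7 gives mutual prediction accuracy a separating role in that comparison. For that to work, a loss of accuracy between cohorts would have to point to one of the two causes of interest.

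It does not. Out-of-sample error contains the irreducible scatter, the estimation error of the fitted model and any true difference between cohorts. Estimation error depends on training size, which here is small by design. A model trained on the late-season cohort can therefore predict a larger study worse than the reverse, even if the two respond identically to identical vaccines. At stake is a formulation or timing difference being read into what is partly a sample-size effect, and a claim about confounding that the analysis cannot support.

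**Working it through.** **Starting point.** The protocol gives no accuracy figure, error metric, number of predictors or residual SD for this analysis, so there is no stated figure to reproduce. The check is whether the mechanism operates at the protocol's own sample sizes, and how strongly.

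**Inputs.** From the protocol: training size n = 25 to 60 (section 9); several day 0 titres as predictors, since section 7 speaks of profiles (number not given). Assumed: residual SD σ = 1.2 log2, comparator n = 200, p = 1 to 8 predictors, ordinary least squares, Gaussian predictors, identical populations, no vaccine effect.

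**Step 1: expected error.** RMSE = σ × √[(1 + 1/n)(n − 2)/(n − p − 2)].

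**Step 2: equivalent shift.** A constant response shift of d log2 adds d² to the mean squared error. The shift that training size imitates is therefore d = √(RMSE²_small − RMSE²_200), or 2^d as a fold change.

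Worked case, p = 8, n = 25: 1.44 × 1.04 × 23/15 = 2.296, RMSE 1.515. At n = 200: 1.44 × 1.005 × 198/190 = 1.508, RMSE 1.228. So d = √(2.296 − 1.508) = 0.888, and 2^0.888 = 1.85.

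| p | RMSE n=25 | RMSE n=60 | RMSE n=200 | Imitated shift, n=25 | Imitated shift, n=60 |
|---|---|---|---|---|---|
| 1 | 1.251 | 1.221 | 1.206 | 1.26-fold | 1.14-fold |
| 2 | 1.281 | 1.231 | 1.209 | 1.34-fold | 1.18-fold |
| 4 | 1.346 | 1.254 | 1.215 | 1.49-fold | 1.24-fold |
| 8 | 1.515 | 1.303 | 1.228 | 1.85-fold | 1.35-fold |

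The n = 200 column is the reverse direction, with the larger study training. Error there is within about 2.3% of the irreducible 1.2 (1.228/1.2 = 1.023), so the penalty is negligible.

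**Step 3: simulation under different assumptions** (ridge fit, p = 10, residual SD 1.0). For two identical cohorts of 40 and 300 with no vaccine effect, RMSE was 1.15 when the small cohort trained and 1.02 when the large one did. The mean signed error was 0.00 both ways, so a signed measure does not share this artefact.

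**Step 4: baseline differences** (same simulation settings, test cohort 2 log2 lower at day 0). If the linear model is correct, RMSE moves from 1.10 to 1.12 at n = 60 and from 1.25 to 1.33 at n = 25. If the true response has a ceiling that the linear model misses, it moves from 1.11 to 1.21 and from 1.27 to 1.41. The loss comes mainly from extrapolation and misspecification.

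**Step 5: assay offset.** If a laboratory reads 1 log2 higher at both visits and fold change falls by 0.4 log2 per log2 of baseline (assumed), the observed day 28 titre rises by 1 and the predicted one by 0.6. About 0.4 log2 remains as signed error. In the simulation RMSE rose from 1.10 to 1.18 (n = 60).

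**The case against.** Five points deserve weight.

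- **Metric and decision rule.** A reader might infer that the plan uses an unsigned error and will credit poor prediction to formulation. The protocol says neither. Section 7 reports a directional result, a roughly twofold lower H3N2 fold change in 2023 than in 2022, and attributes it to immune background because the strain was unchanged. The choice of metric could properly sit in an analysis plan not shown here. What stands is that section 7 itself names accuracy as a means of separating the two effects.
- **Other evidence.** Accuracy accompanies direct day 28 and day 90 comparisons, and the two 2023-vaccine cohorts form a pair with no composition change. This is a real design strength, but a partial control: training size, vaccination history and laboratory may differ between pairs.
- **Direction.** The models are described as trained on earlier studies, where the penalty almost vanishes. True, but section 7 has each cohort predicting the others, so this cohort also trains.
- **Size.** A reader might infer that the artefact rivals the twofold gap in section 7. Only many predictors at the enrolment floor come near it; most of the range is well below.
- **Assays and baseline.** A reader might infer a large laboratory artefact. The protocol does not say that assays differ, and an offset on both visits largely cancels in fold change. Baseline differences are also part of the exposure background under study; they mislead only when the gap is read as composition.

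**Conclusion.** The point holds in a limited form. Raw transfer accuracy is not specific to composition or exposure background, so on its own it cannot support the separation that section 7 promises or the statement "rigorously assess vaccine responses across seasons without the confounding effects of different immune backgrounds". The firmest driver is training size. It imitates a 1.26- to 1.85-fold shift at n = 25 and a 1.14- to 1.35-fold shift at n = 60, and only when this cohort trains the model. These sizes rest on the assumed SD, comparator size, predictor count and least-squares fit; the direction does not. Prior-vaccination differences can add to the gap through extrapolation. Assay differences are a possibility, not a documented fact. The documents do not support saying that the whole cross-cohort comparison fails, or that the plan commits to a false attribution. This is an inexpensive improvement to a stated inference.

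**What to change.** 1. Compare each cross-cohort error with within-cohort cross-validated error at matched training size, for example by repeatedly subsampling the larger study to this cohort's n.
2. Report the signed mean offset and calibration slope on the log2 scale, with bootstrap intervals, within the range of baseline titres that the cohorts share.
3. Use the same-formulation pair (fall 2023 and late-season 2023), plus pairs of earlier studies from one season where they exist, as the no-composition-change reference. Credit formulation only for an offset beyond that reference. This step is also the guard against an assay offset, which the signed measure alone does not remove.
4. If these steps are not taken, soften the section 7 wording on disentangling the two effects and on freedom from confounding.

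The cost is extra analysis and a more cautious claim. No added participants, visits or samples are needed. The protocol does not confirm that every season has more than one study, so the reference in step 3 may be thin.

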Please note: In the case of NIH-funded human subjects research, all individuals who are involved with the design or conduct of the research must complete Human Subjects Training

5. Biospecimens/Data

Biospecimens and/or data will be collected specifically for this research project

Yes No

Existing biospecimens and/or data will be used for this project

Yes No

List the materials from human subjects (this may include specimens, records, or data) that will be utilized for this project.

Type of Samples	Source of Samples
Example: Blood samples	Collected by clinical collaborators at University of Virginia
Blood samples	Collected by the LJI Clinical Core

6. Specific Aims

Briefly describe the purpose, specific aims, or objectives of the study. State the hypotheses to be tested. Emphasize those aspects that justify the use of human subjects.

Aim 1: Do the 2023 and 2024 influenza vaccine formulations elicit markedly different antibody responses? Influenza vaccines are primarily assessed by measuring how potently an individual's serum inhibits hemagglutination of different influenza variants. We will administer the FluZone, an approved seasonal influenza vaccine with demonstrated efficacy in adults, and collect serum from each vaccinee at day 0 (right before vaccination), day 28 (the peak vaccine response), and day 90 (to test how rapidly their antibody response wanes). Previous vaccine studies have shown that updating the seasonal vaccine leads to different antibody responses. Our cohort will identify whether such differences arise from different exposure histories or from the different vaccine formulations.

Aim 2: Does administering the 2023 vaccine in the fall versus later in the season affect the subsequent antibody response? By comparing antibody responses in our cohort versus responses from influenza vaccine studies carried out in September-November 2023, we will quantify whether administering the vaccine 6-8 months later leads to fundamentally different responses. If vaccine responses look identical, it will obviate the need for late-season vaccine studies, whereas if they look markedly different it will emphasize a need to decouple exposure background from vaccine responses when comparing results across years.

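### Sections 6 and 7 claim to separate formulation from exposure history, but the cohort has no 2023-24 dose and the fall 2024 comparators have no stated history restriction; the two groups named for Aim 4 cannot isolate the late dose

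*Protocol*

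**What the plan says.** Section 6, Aim 1, promises a separation of causes: "Our cohort will identify whether such differences arise from different exposure histories or from the different vaccine formulations". Section 7 names three sets of data: fall 2023 studies of the 2023 vaccine, the late-season cohort, and "future vaccine studies next fall administering the 2024 vaccine". It plans to see how well each cohort predicts the others "to disentangle the effects of exposure background and vaccine composition", and concludes that "we will demonstrate a means to rigorously assess vaccine responses across seasons without the confounding effects of different immune backgrounds".

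Who is in the cohort is fixed elsewhere. An exclusion criterion in section 9 is "Received an influenza vaccine in the past year", and the pre-screening questions in section 10 turn away anyone vaccinated in 2023-24. No matching restriction or stratification is stated for the fall 2024 studies.

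For Aim 4, only people who had the late-season dose may continue (section 9, June 2024 amendment). Section 6 sets them against "responses from other influenza vaccine studies (where participants are annually vaccinated"), and section 7 describes the comparators' previous dose as given "in the Fall of 2023 [using other annual vaccine studies"]. The amendment in section 7 then states: "Our goal will be to demonstrate whether such late-season vaccine administration can boost subsequent vaccine responses".

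**The concern.** The argument of Aim 1 needs the late-season cohort and the fall 2024 recipients to share an exposure background, so that formulation is what differs. The eligibility rule works against this: everyone in the cohort lacks a 2023-24 dose, and an unknown part of the comparators will have had one. Section 7 itself holds that immune background can substantially affect the response.

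Two misreadings could follow. A difference between the cohort and the fall 2024 studies could be reported as a formulation effect when it partly reflects a recent dose in the comparators only. A difference in Aim 4 could be reported as priming by late-season vaccination when it partly reflects who skips the fall dose.

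**Working it through.** The protocol gives no figure to reproduce here. The question is what the named groups can estimate, so I set out their histories and write each contrast as a simple additive model.

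| Group | Vaccine studied | Fall 2023 dose beforehand | Late-season dose beforehand |
|---|---|---|---|
| Cohort, first vaccination | 2023 | none (sections 9, 10) | none |
| Fall 2024 studies (Aim 1) | 2024 | not restricted (section 7) | none stated |
| Cohort, second vaccination | 2024 | none | all (section 9 amendment) |
| Annual vaccinees (Aim 4) | 2024 | all (sections 6, 7) | none stated |

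**Aim 1.** Let f be the effect of the 2024 formulation, h the effect of a fall 2023 dose on the later response, and p the share of comparators with that dose.

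- Cohort mean: a. Comparator mean: a + f + p × h.
- Difference: f + p × h, so the bias for f is p × h. It runs from nothing at p = 0 to all of h at p = 1.
- If every comparator had the dose, the design rows (intercept, formulation, prior dose) are (1,0,0) and (1,1,1). The rank is 2 for 3 parameters, and only f + h can be estimated.
- Comparators with no 2023-24 dose contribute the row (1,1,0). The rank becomes 3, and their difference from the cohort is f.

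The fall 2023 arm does not fill the gap by itself. It holds formulation fixed, but for its participants the fall 2023 dose is the dose under study, not one received beforehand. It can inform h only if an earlier season's dose is assumed to act in the same way and timing is assumed not to matter.

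**How far the Aim 1 histories differ.** I take fall as September to November, and consider a cohort member last vaccinated in fall 2022. The share of such members is not given.

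- Cohort member, fall 2022 to 1 May-30 June 2024: 518 to 668 days, midpoint (518 + 668)/2 = 593.
- Fall 2024 comparator with a fall 2023 dose: 276 to 456 days, midpoint 366. Gap: 593 − 366 = 227 days.
- Fall 2024 comparator with no 2023-24 dose, last vaccinated in fall 2022: 641 to 821 days, midpoint 731. Gap: 731 − 593 = 138 days.

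Restricting the comparators brings the histories closer but leaves a lag. These are descriptions of history, not effects on titre.

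**Aim 4.** Let k be the effect of a fall 2023 dose, together with the annual habit that goes with it in these comparators, and l the effect of the late dose.

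- Cohort mean: a + l. Comparator mean: a + k. Difference: l − k.
- Rows (intercept, fall 2023 dose, late dose) are (1,0,1) and (1,1,0): rank 2 for 3 parameters. No model fitted to these two groups alone gives l.
- A third group given the 2024 vaccine, with neither a fall 2023 dose nor a late dose, adds (1,0,0). The rank becomes 3, and cohort minus third group gives l among people who skipped the fall dose.

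**The case against.** The best defence is that the protocol does plan for background differences. It has the fall 2023 arm, which varies background with formulation fixed, and it predicts responses from day 0 antibody profiles. Comparator selection and matching are often left to an SAP, which is not at hand, and the fall 2024 studies had not yet been run. All this is fair, and these steps may reduce the bias. But nothing shows that they remove the prior-dose difference, and the two sentences promise that it will be gone.

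For Aim 4 it can be said that lacking a fall 2023 dose belongs to the regimen being studied. That stands for a comparison of whole regimens. It does not support attributing the difference to late administration, because the groups also differ in who skips and who vaccinates every year.

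Three stronger readings are tempting, and the documents do not support them:

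- *That Aim 4 can never be rescued.* This is true only of the two groups named. The unrestricted fall 2024 studies may contain the missing third group.
- *That the dose intervals in Aim 4 show bias.* From the protocol's dates, the cohort's two doses lie about 76 to 213 days apart (the minimum is 90 − 14, as the day 90 visit comes first), and the comparators' 276 to 456 days. Not overlapping is what late versus fall means; it is the intended contrast.
- *That the bias is about two-fold.* Section 7 reports an H3N2 fold-change about 2x lower with the 2023 than with the 2022 vaccine, the strain being the same. It attributes this to immune background in general, not to a prior-season dose, so it cannot serve as an estimate of h.

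**Conclusion.** The point holds, and should be settled before comparators are chosen. The statements that the cohort will identify the cause, and that immune-background confounding will be absent, go beyond what the described comparisons can deliver. In Aim 1 the bias is p × h; both terms are unknown, so neither size nor direction can be given. In Aim 4 the two named groups yield only l − k, so a difference between them cannot be credited to late timing alone.

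This rests on reading the eligibility rules as written, on additive effects in the models above, and on at least some fall 2024 comparators having had a fall 2023 dose. A reader might infer that Aim 1 will give a wrong answer. The documents do not show that; they show only that the promised separation is not secured.

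**What to change.** 1. **Aim 1.** Make the main comparison with fall 2024 recipients aged 18-64 who had no 2023-24 dose. Stratify by or adjust for 2022-23 vaccination (yes/no) and day 0 log2 titre. The section 10 items ask yes/no and route by season, not dates, so time since last dose should not be promised as a covariate. If the external data do not record history, state that formulation and a 2023-24 dose cannot be separated.
2. **Aim 4.** Where available, add the same people (2024 vaccine, no fall 2023 dose, no late dose) as a second comparator. Keep the comparison with annual vaccinees as one of whole regimens, and do not attribute that difference to late timing alone. Show results with and without day 0 titre: in the cohort it is measured after the late dose, so adjusting for it may remove part of the effect sought.
3. **Wording.** In Aim 1, write that the cohort *will help assess whether* the differences have one source or the other. In section 7, replace the closing no-confounding phrase with *accounting, where recorded, for vaccination history and baseline titre*.

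The changes need no new visits or samples, and the cohort is already asked about 2022-23 vaccination. The cost is fewer usable external comparators and wider intervals, since studies without recorded history drop out of the main comparison. Differences in season, study and laboratory remain and should be stated as limits.
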